#### 5.4.2. Responsibilities

(Amended 12 December 2016)

The overall responsibility of the IDMC is to protect the ethical and safety interests of *subjects* recruited into this study while protecting as far as possible the scientific validity of the data.

The details of the IDMC's responsibilities and conduct of meetings will be provided in the IDMC charter. The IDMC charter will also clearly state who will conduct the statistical analysis (ICH E9). Key responsibilities of the IDMC are the following:

- Prior to study start, the IDMC will review the protocol with special attention to safety monitoring procedures and will make recommendations for adjustments, if required.
- ***The IDMC will be informed of any amendment to the initial protocol***
- The IDMC will review the ***unblinded*** safety data from the study (i.e., each SAE, grade 3 local and general solicited AEs, unsolicited AEs ***and neurodevelopmental status***), provide GSK Biologicals with indications on safety profiles and make recommendations on further study conduct.
- The IDMC will review the final analysis provided by the sponsor.

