**Table 11 Solicited local adverse events**

Pain at injection site
Redness at injection site
Swelling at injection site

N.B. If parent(s)/LAR(s) of infants observe any large injection site reaction [defined as any local swelling with diameter > 50 mm and/or any noticeable diffuse injection site swelling (diameter not measurable) and/or any noticeable increased circumference of the injected limb)], they will be asked to contact the study personnel and bring the subject for an evaluation by the investigator as soon as possible. The investigator will record detailed information describing the AE on a specific large swelling reaction sheet in the eCRF.

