**Table 14 Intensity scales for solicited symptoms**

Adverse Event	Intensity grade	Parameter
Pain at injection site	0	None
	1	Mild: Minor reaction to touch
	2	Moderate: Cries/protests on touch
	3	Severe: Cries when limb is moved/spontaneously painful
Redness at injection site		Record greatest surface diameter in mm
Swelling at injection site		Record greatest surface diameter in mm
Fever*		Record temperature in °C/°F
Irritability/Fussiness	0	Behaviour as usual
	1	Mild: Crying more than usual/no effect on normal activity
	2	Moderate: Crying more than usual/interferes with normal activity
	3	Severe: Crying that cannot be comforted/prevents normal activity
Drowsiness	0	Behaviour as usual
	1	Mild: Drowsiness easily tolerated
	2	Moderate: Drowsiness that interferes with normal activity
	3	Severe: Drowsiness that prevents normal activity
Loss of appetite	0	Appetite as usual
	1	Mild: Eating less than usual/no effect on normal activity
	2	Moderate: Eating less than usual/interferes with normal activity
	3	Severe: Not eating at all

\*Fever is defined as temperature  $\geq 37.5^{\circ}\text{C}/99.5^{\circ}\text{F}$  for oral, axillary or tympanic route, or  $\geq 38.0^{\circ}\text{C}/100.4^{\circ}\text{F}$  for rectal route. The preferred route for recording temperature in this study will be axillary/rectal.

The maximum intensity of local injection site redness/swelling will be scored at GSK Biologicals as follows:

- 0 : Absent
- 1 :  $\leq 5$  mm
- 2 :  $> 5$  mm and  $\leq 20$  mm
- 3 :  $> 20$  mm

The maximum intensity of fever (*oral, axillary or tympanic route*) will be scored at GSK Biologicals as follows: (Amended 12 December 2016)

- 0 =  $< 37.5^{\circ}\text{C}$
- 1 =  $\geq 37.5^{\circ}\text{C}$  to  $\leq 38.0^{\circ}\text{C}$
- 2 =  $> 38.0^{\circ}\text{C}$  to  $\leq 39.0^{\circ}\text{C}$
- 3 =  $> 39.0^{\circ}\text{C}$

The investigator will assess the maximum intensity that occurred over the duration of the event for all unsolicited AEs (including SAEs) recorded during the study. The assessment will be based on the investigator's clinical judgement.

The intensity should be assigned to one of the following categories:

- 1 (mild) = An AE which is easily tolerated by the subject, causing minimal discomfort and not interfering with everyday activities.
- 2 (moderate) = An AE which is sufficiently discomforting to interfere with normal everyday activities.

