- The verbatim reports of unsolicited AEs will be reviewed by a physician and the signs and symptoms will be coded according to MedDRA. Every verbatim term will be matched with the appropriate Preferred Term. The percentage of subjects with unsolicited AEs occurring within 31-day (Day 0- Day 30) follow-up period after any dose with its exact 95% CI [Clopper, 1934] will be tabulated by group, and by preferred term. Similar tabulation will be done for unsolicited AEs rated as grade 3, for unsolicited AEs with causal relationship to vaccination and AEs/SAEs leading to withdrawal from the study.
- The percentage of subjects who receive concomitant medication and antipyretic medication during the 4-day (Day 0- Day 3) follow-up period and during the entire

study period will be tabulated (with exact 95% CI [Clopper, 1934]) after the booster dose.

- Any large injection site reaction (defined as any local swelling with diameter > 50 mm and/or any noticeable diffuse injection site swelling (diameter not measurable) and/or any noticeable increased circumference of the injected limb) reported within 4 days (Day 0-Day 3) following the booster dose will be described in detail.
- Subjects who experience at least one SAE from booster vaccination up to study end will be described in detail.
- Subjects who report at least one SAE after the end of primary study 201330 [DTPA (BOOSTRIX)-048 PRI] and before 201334 [DTPA (BOOSTRIX)-049 BST: 048] study will be described in detail.
- Withdrawal due to AEs and SAEs following vaccinations will be described in detail.
- For the subjects who withdraw from the study after Visit 1 (after completion of ASQ-3 questionnaire but have not received booster vaccination), the analysis will be performed on the Total enrolled cohort.
- Neurodevelopmental status of the subjects will be assessed depending on the ASQ-3 score. The proportion of subjects in the black zone for any domain, for gross motor skills, fine motor skills, communication, problem solving skills and personal-social skills will be tabulated. The proportion of infants referred for formal neurodevelopmental evaluation using BSID-III and those with at least one indicators of neurodevelopmental impairment using BSID-III will also be tabulated.

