10.1.2.3.2. Studies with paper diaries

For studies using paper diaries which have questions in the CRF indicating the presence or absence of solicited symptoms, the following rules are applicable.

Denominators for the summary of local (or general) solicited symptoms will be calculated using the number of subjects who respond "Yes" or "No" to the question concerning the occurrence of local (or general) symptoms.

When a specific symptom is marked as having not occurred following a specific vaccination for the specified post-vaccination period for the symptom in question, all daily measurements will be imputed as Grade 0.

When a specific symptom is marked as having occurred following a specific vaccination for the specified post-vaccination period for the symptom in question, any missing daily recordings will be given imputed values to allow them to contribute to the ‘Any’ rows but not to specific grade rows of the symptom summary tables.

When the occurrence of a specific symptom is not present (for the specified post-vaccination period for the symptom in question) but the group of symptoms (local or general) is marked as having occurred, all missing daily recordings will be given imputed values to allow them to contribute to the ‘Any’ rows but not to specific grade rows of the symptom summary tables.

The following table shows how subjects contribute to each category for a specific solicited symptom over the Day 0 to Day 3 post-vaccination period:

Solicited symptom category	Subjects included in the calculation of the numerator
Any	All subjects with at least one occurrence of the symptom at grade 1, grade 2, or grade 3 between Day 0 and Day 3 or with the symptom marked as present and at least one missing daily recording between Day 0 and Day 3
At least grade 1	All subjects with at least one occurrence of the symptom at grade 1, grade 2, or grade 3 between Day 0 and Day 3
At least grade 2	All subjects with at least one occurrence of the symptom at grade 2 or grade 3 between Day 0 and Day 3
At least grade 3	All subjects with at least one occurrence of the symptom at grade 3 between Day 0 and Day 3

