For a given subject and the analysis of solicited adverse events within 4 days post-vaccination, missing or non-evaluable measurements will not be replaced. Therefore, the analysis of the solicited adverse events based on the Total Vaccinated Cohort will include only vaccinated subjects for doses with documented safety data (i.e., symptom screen completed). More specifically the following rules will be used:

- Subjects who documented the absence of a solicited adverse events after one dose will be considered not having that adverse events after that dose.
- Subjects who documented the presence of a solicited symptom and fully or partially recorded daily measurement over the solicited period will be included in the summaries at that dose and classified according to their maximum observed daily recording over the solicited period.
- Subjects who documented the presence of a solicited symptom after one dose without having recorded any daily measurement will be assigned to the lowest intensity category at that dose (i.e., 37.5°C for fever or grade 1 for other symptoms).
- Doses without symptom sheets documented will be excluded.

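### Solicited swelling is graded only by diameter in mm, so a diffuse or limb-wide swelling without a recorded diameter above 20 mm cannot count as grade 3

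*Protocol*

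**What the plan says.** **Grading.** For swelling, Table 14 in protocol 8.2.3.2.1 has one instruction: "Record greatest surface diameter in mm". Below the table, "The maximum intensity of local injection site redness/swelling will be scored at GSK Biologicals as follows": 0 if absent, 1 up to 5 mm, 2 above 5 and up to 20 mm, 3 above 20 mm. There is no category for swelling that has no diameter.

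**Large reactions.** The note under Table 11 (protocol 8.1.3.1), repeated in protocol 10.8 and SAP 5.4.1, defines a large injection site reaction as a swelling wider than 50 mm and/or "any noticeable diffuse injection site swelling (diameter not measurable) and/or any noticeable increased circumference of the injected limb". Parents are to bring such an infant for evaluation, and "The investigator will record detailed information describing the AE on a specific large swelling reaction sheet in the eCRF".

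**Missing daily values.** SAP 10.1.2.3.2 gives two sets of rules.

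- The rules before its numerator table say that a symptom marked present with missing daily recordings contributes to the Any "rows but not to specific grade rows of the symptom summary tables". In the table, the grade 3 numerator is "All subjects with at least one occurrence of the symptom at grade 3 between Day 0 and Day 3".
- The bullets after the table say that a subject with the symptom present but "without having recorded any daily measurement will be assigned to the lowest intensity category at that dose", which is grade 1 for swelling. A subject with partial recordings is classed by the largest value observed.

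**Outputs.** Protocol 10.8 and SAP 5.4.1 plan percentages with exact 95% confidence intervals for each solicited symptom, also at grade 2 or above and at grade 3, and for any local symptom at grade 3. Among the data that the IDMC reviews, protocol 5.4.2 names "each SAE, grade 3 local and general solicited AEs, unsolicited AEs".

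**The concern.** The protocol puts an unmeasurable diffuse swelling in the same class as a swelling wider than 50 mm. The measured member of that class is grade 3, because 50 mm is well above the 20 mm limit. The unmeasurable member has no route to grade 3 of its own, and the missing-value rules give it the mildest grade or none.

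This missingness is informative. The diameter may be absent because the swelling has no clear edge or involves the limb, not because a diary entry was forgotten. A rule meant for incomplete diaries then handles it as if it were mild. Any resulting error in the graded rates goes one way, downward. Nothing in either document says that the large swelling reaction sheet feeds the solicited swelling grade.

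**Working it through.** **1. Apply the rules to test patterns.** The inputs are the bands under Table 14 and the two rule sets in SAP 10.1.2.3.2. In each pattern swelling is marked present; a dash means no diameter was recorded that day.

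| Days 0, 1, 2, 3 (mm) | Rules before the numerator table | Bullets after the table |
|---|---|---|
| –, –, –, – | Any only, no grade | Grade 1 |
| 4, –, –, – | Grade 1 | Grade 1 |
| 15, –, –, – | Grade 2 | Grade 2 |
| 25, –, –, – | Grade 3 | Grade 3 |
| 60, 60, 40, 10 | Grade 3 | Grade 3 |

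Three results follow.

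- An unmeasured day never produces grade 3. Only a recorded value above 20 mm on at least one of the four days does so.
- The grade 2-or-above row is affected only when no recorded value exceeds 5 mm (first two patterns). The grade 3 row is affected when none exceeds 20 mm (first three).
- The two rule sets disagree on the first pattern. That conflict exists for any solicited symptom marked present without daily values, not only for swelling.

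The grade 3 any-local-symptom row changes only if the infant has no other grade 3 local symptom, such as pain.

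**2. Reproduce the plan's figures.** Template 18 in the SAP has filled-in swelling counts. The SAP says its templates were copied from recent studies and are for illustration, so these are not trial results. With x events in n subjects, the Clopper-Pearson 95% limits are the 0.025 quantile of Beta(x, n − x + 1) and the 0.975 quantile of Beta(x + 1, n − x).

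- Grade 3 swelling: 6/330 = 1.8% (0.7 to 3.9) and 5/329 = 1.5% (0.5 to 3.5).
- All swelling: 98/330 = 29.7% (24.8 to 34.9) and 90/329 = 27.4% (22.6 to 32.5).

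All four agree with the template.

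**3. Illustrate sensitivity.** Let k be the number of infants in a group with an unmeasurable large swelling and no recorded value above 20 mm. The documents do not give k, so it is an assumption. Counting those infants as grade 3 gives (6 + k)/330 in the dTpa shell:

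| k (assumed) | Count | Rate, 95% CI |
|---|---|---|
| 0 | 6/330 | 1.8% (0.7 to 3.9) |
| 1 | 7/330 | 2.1% (0.9 to 4.3) |
| 3 | 9/330 | 2.7% (1.3 to 5.1) |
| 6 | 12/330 | 3.6% (1.9 to 6.3) |
| 10 | 16/330 | 4.8% (2.8 to 7.8) |

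In the Control shell, k = 3 gives 8/329 = 2.4% (1.1 to 4.7). Under the SAP's present rules the reported rates stay at 1.8% and 1.5% whatever k is.

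**The case against.** **What is entered is not stated.** Table 14 asks for a diameter without exception, the infant is to be seen by the investigator, and diary cards are verified at Visit 3. A diameter may therefore be recorded even for a diffuse swelling. This stands: the point is conditional on no value above 20 mm being entered. The protocol's own wording, however, allows for a swelling whose diameter cannot be measured.

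**A reader might infer that the most extensive reactions as a class leave the grade 3 rate, or leave the report.** The documents do not support either. Every swelling measured above 50 mm is grade 3, as is any with one recorded day above 20 mm. The unmeasurable cases still count in the Any row. They are described in detail (protocol 10.8, SAP 5.4.1), have their own listing (Template 28 in the SAP's list of templates) and have their own code in the combined adverse event summary (SAP 5.4.2.1). The loss is confined to graded rows. A narrative does not correct a percentage and its interval, but nothing is hidden.

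**The IDMC is not dependent on the graded row.** Protocol 5.4.1 gives it all relevant safety data and access on request. This stands, so oversight adds little weight.

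**A reader might put a size on the bias.** Suppose 1% to 3% of 335 infants per group have a large reaction and 20% to 50% of those are unmeasurable. Then 335 × 0.01 × 0.20 = 0.7 and 335 × 0.03 × 0.50 = 5.0 infants, or 0.2 to 1.5 percentage points. Against a supposed 5% grade 3 rate that is a 4% to 30% relative understatement. Both frequencies and the 5% are guesses, 335 is a mock-table number, and the product assumes that none of these infants has a value above 20 mm. It cannot be given as a finding.

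**Scoring every such case grade 3 could overgrade.** The definition covers any noticeable diffuse swelling or limb enlargement, with no size threshold, and groups these reactions for reporting rather than for intensity. This stands, and is why the remedy shows the rate both ways.

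**The analyses are descriptive and the rule is the same in both groups.** True, and it limits the consequence. Each group's rate is still reported in its own right.

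**Conclusion.** The gap is real and follows from the documents' own rules. A scale that accepts only diameters meets a reaction defined partly by having none, and the missing-value rules resolve this toward grade 1 or no grade. The bias can only be downward. It is limited to diffuse or limb-wide swellings with no recorded value above 20 mm on Days 0 to 3, and to the graded swelling and grade 3 local-symptom rows. Its size cannot be derived, because neither the frequency of such reactions nor the data-entry practice is stated; the table above shows only how sensitive a small grade 3 count is. The conflict between the two rules in SAP 10.1.2.3.2 needs no such assumption. The change is worth making because it is cheap, although it concerns a secondary, descriptive safety endpoint.

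**What to change.** In SAP 10.1.2.3.2:

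1. Reconcile the two rule sets, so that a symptom marked present with no daily value has one stated outcome.
2. State that the lowest-intensity rule does not apply to a swelling recorded on the large swelling reaction sheet as diffuse or not measurable, or as increased limb circumference.
3. Report grade 3 swelling, with its exact interval, both with these subjects counted as grade 3 and without them. Alternatively, add a separate row for large, not measurable swelling beside grade 3.

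The cost is a short SAP amendment and a programming link to an eCRF sheet that is already collected. The grade 3 rate may look slightly less favourable.

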#### **8.2.3.2.2. Assessment of causality**

The definitions for 'NO' and 'YES' have been written in such a way that all events that have been attributed a 'NO' can be pooled with events which in the primary vaccination study were determined to be 'not related' or 'unlikely to be related' to vaccination. Those events that are attributed a 'YES' can be pooled with those events that in the past were determined to have a 'suspected' or 'probable' relationship to vaccination in the primary vaccination study.

The investigator is obligated to assess the relationship between investigational vaccine and the occurrence of each AE/SAE. The investigator will use clinical judgement to determine the relationship. Alternative plausible causes, such as natural history of the underlying diseases, concomitant therapy, other risk factors, and the temporal relationship of the event to the investigational vaccine will be considered and investigated. The investigator will also consult the IB and/or *PI* for marketed products to determine his/her assessment. **(Amended 12 December 2016)**

There may be situations when a SAE has occurred and the investigator has minimal information to include in the initial report to GSK Biologicals. However, it is very important that the investigator always makes an assessment of causality for every event prior to submission of the Expedited Adverse Events Report to GSK Biologicals. The investigator may change his/her opinion of causality in light of follow-up information and update the SAE information accordingly. The causality assessment is one of the criteria used when determining regulatory reporting requirements.

In case of concomitant administration of multiple vaccines/products, it may not be possible to determine the causal relationship of general AEs to the individual vaccine

administered. The investigator should, therefore, assess whether the AE could be causally related to vaccination rather than to the individual vaccines.

All solicited local (injection site) reactions will be considered causally related to vaccination. Causality of all other AEs should be assessed by the investigator using the following question:

*Is there a reasonable possibility that the AE may have been caused by the investigational vaccine?*

- YES : There is a reasonable possibility that the vaccines contributed to the AE.
- NO : There is no reasonable possibility that the AE is causally related to the administration of the study vaccines. There are other, more likely causes and administration of the study vaccines is not suspected to have contributed to the AE.

If an event meets the criteria to be determined as ‘serious’ (see Section 8.1.2), additional examinations/tests will be performed by the investigator in order to determine ALL possible contributing factors for each SAE.

Possible contributing factors include:

- Medical history.
- Other medication.
- Protocol required procedure.
- Other procedure not required by the protocol.
- Lack of efficacy of the vaccines, if applicable.
- Erroneous administration.
- Other cause (specify).

#### **8.2.3.3. Assessment of outcomes**

The investigator will assess the outcome of all unsolicited AEs (including SAEs) recorded during the study as:

- Recovered/resolved.
- Recovering/resolving.
- Not recovered/not resolved.
- Recovered with sequelae/resolved with sequelae.
- Fatal (SAEs only).

**8.2.3.4. Assessment of neurodevelopmental status**

The parent(s)/LAR(s) will be asked to complete a standardised developmental screening tool known as ASQ-3. Refer to Section 5.6.2.13 for more details.

**8.2.3.5. Medically attended visits**

For each solicited and unsolicited symptom the subject experiences, the subject’s parent(s)/LAR(s) will be asked if the subject received medical attention defined as hospitalisation, or an otherwise unscheduled visit to or from medical personnel for any reason, including emergency room visits. This information will be recorded in the eCRF.

**8.3. Reporting of serious adverse events**

**8.3.1. Prompt reporting of serious adverse events to GSK Biologicals**

SAEs that occur in the time period defined in Section 8.2 will be reported promptly to GSK within the timeframes described in Table 15, once the investigator determines that the event meets the protocol definition of a SAE.

**Table 15 Timeframes for submitting serious adverse event reports to GSK Biologicals**

Type of Event	Initial Reports		Follow-up of Relevant Information on a Previous Report	
	Timeframe	Documents	Timeframe	Documents
SAEs	24 hours*‡	electronic Expedited Adverse Events Report	24 hours*	electronic Expedited Adverse Events Report

\* Timeframe allowed after receipt or awareness of the information.

‡ The investigator will be required to confirm review of the SAE causality by ticking the ‘reviewed’ box in the electronic Expedited Adverse Events Report within 72 hours of submission of the SAE.

**8.3.3. Completion and transmission of SAE reports to GSK Biologicals**

Once an investigator becomes aware that a SAE has occurred in a study subject, the investigator (or designate) must complete the information in the electronic Expedited Adverse Events Report WITHIN 24 HOURS. The report will always be completed as thoroughly as possible with all available details of the event. Even if the investigator does

not have all information regarding a SAE, the report should still be completed within 24 hours. Once additional relevant information is received, the report should be updated WITHIN 24 HOURS.

The investigator will always provide an assessment of causality at the time of the initial report. The investigator will be required to confirm the review of the SAE causality by ticking the 'reviewed' box in the electronic Expedited Adverse Events Report within 72 hours of submission of the SAE.

